#### Scatter plots to support vital sign evaluations

Scatter plots of maximum-by-maximum measurements and minimum-by-minimum measurements will not be created a-priori. They may be created if warranted after review of the planned tables and figures, using Figures 6.3 and 6.4 from the Analysis and Displays for Labs

white paper (PHUSE 2022) as the model. ADaM datasets will include variables to enable the creation of scatter plots for use in either an interactive tool or for ad-hoc figures.

#### 4.6.3. Device Product Complaints

A summary of all product complaints, inclusive of device product complaints that lead to an AE and/or SAE will be included by category. Additional summaries may be provided as deemed appropriate.

### 4.7. Other Analyses

#### 4.7.1. Immunogenicity

A participant is evaluable for TE ADA if the participant has a non-missing baseline ADA result, and at least 1 non-missing postbaseline ADA result.

A participant who is evaluable for TE ADA is TE ADA+ if either of the following holds:

- Treatment-induced ADA: the participant has baseline status of ADA Not Present and at least 1 postbaseline status of ADA Present with titer  $\geq 1:40$ , which is  $2 \times$  minimum required dilution (MRD) of the ADA assay (MRD=1:20).
- Treatment-boosted ADA: the participant has baseline status of ADA Present and at least 1 postbaseline status of ADA Present with the titer being  $\geq 2$  dilutions (4-fold) of the baseline titer. That is, the participant has baseline (B) status of ADA Present, with titer 1:B, and at least 1 postbaseline (P) status of ADA Present, with titer 1:P and  $P/B \geq 4$ .

All analyses will be based on all evaluable TE ADA participants. The baseline ADA status will be summarized by treatment group. The number and percentage of participants who are TE ADA+ will be summarized by treatment group. The summary will include the number and percentage of participants with treatment-induced ADA and treatment boosted ADA. A summary of titer values will be provided for participants who are TE ADA positive. This analysis will be performed for the following periods:

- The treatment period up to treatment discontinuation
- The entire postbaseline period, including safety follow-up

A number of additional analyses of the immunogenicity data from this study will be presented in an integrated summary document, alongside data from other studies. The analyses to be performed are described in the PSAP.

#### 4.7.2. Subgroup Analyses

The interaction effects will be evaluated using a significance level of 0.05, unadjusted. Subgroup analyses will be conducted as defined in this section. Additional subgroup analysis may also be performed as appropriate.

##### 4.7.2.1. Subgroups Analysis for HbA1c:

The subgroups for analyzing HbA1c and change in HbA1c from baseline to Week 26 will be defined as:

- Baseline HbA1c stratum ( $<8.0\%$  and  $\geq 8.0\%$ )
- Routine use of personal CGM or FGM at randomization (Yes or No)
- Region
  - US and non-US
  - North America, South America, Europe, Asia
- Type of pre-study basal insulin (typical once-daily basal insulin and U-300/NPH BID regimens)
- Prandial insulin dosing plan (carbohydrate counting: Yes or No)
- Use of correction factor (Yes or No)
- Age group:  $<65$  years and  $\geq 65$  years
- Sex (Male and Female)
- Ethnicity (Hispanic or Latino, Not Hispanic or Latino, Not Reported)
- Race (White, Asian, American Indian or Alaska Native, Black or African American )
- Glucagon-like peptide 1 (GLP-1) usage at baseline (Yes and No)
- Estimated Glomerular Filtration Rate (eGFR) at baseline ( $<30$ ,  $\geq 30$  to  $<60$ ,  $\geq 60$  to  $<90$  and  $\geq 90$  mL/min/1.73 m^2), and
- Duration of diabetes ( $<$  median and  $\geq$  median).

Analyses for HbA1c and its change will be performed within each subgroup using the same MMRM model for efficacy estimand described for the primary analysis in Section 4.3.2. In addition, the interaction effects will be assessed using the model including the same fixed effects given for the primary analysis model plus factors of subgroup, 2-way interaction of subgroup and treatment, 2-way interaction of subgroup and visit, and 3-way interaction of treatment, visit and the subgroup.

The ANCOVA analysis for HbA1c for the treatment regimen estimand as described in Section 4.3.2 will be performed within each subgroup. The statistical inference will be based on the multiple imputation framework by Rubin (1987). The p-value for treatment by subgroup interaction will be calculated using a z-test for variables with 2 subgroups and chi-square test for variables with 3 subgroups based on estimated treatment differences within each subgroup. (See details in Appendix 12 [Section 6.12]).

#### 4.7.2.2. Subgroup Analysis for Participant-Reported Hypoglycemic Events

The subgroups, for analyzing documented Level 2/3 hypoglycemia, non-nocturnal and nocturnal hypoglycemia rates during 0-26 weeks, will be defined as:

- Baseline HbA1c stratum (<8.0% and  $\geq$ 8.0%)
- Routine use of personal CGM or FGM at randomization (Yes or No)
- Region
  - US and non-US
  - North America, South America, Europe, Asia
- Type of pre-study basal insulin (typical once-daily basal insulin and U-300/NPH BID regimens)
- Age group: <65 years and  $\geq$ 65 years
- Estimated Glomerular Filtration Rate (eGFR) at baseline : (<60,  $\geq$ 60 to <90 and  $\geq$ 90 mL/min/1.73 m^2)
- Glucagon-like peptide 1 (GLP-1) usage at baseline (Yes and No)
- Number of prandial insulin injection/day at baseline (2 and  $>$ 2)

The hypoglycemia rates will be analyzed using a negative binomial regression including the same independent variables for hypoglycemia event analyses (see Section [4.6.2.2](#)) plus factors of subgroup, 2-way interaction of subgroup and treatment.

### 4.8. Interim Analyses

#### 4.8.1. Data Monitoring Committee

An independent external data monitoring committee (DMC) will be responsible for reviewing unblinded data during the study. The committee will include 4 clinicians and 1 statistician who are independent experts not involved in the study. The DMC will review unblinded safety data to ensure the safety of study participants and some efficacy data to confirm a reasonable risk-benefit profile. A subset of analyses described above in Sections [4.3](#), [4.4](#), [4.5](#), and [4.6](#) will be provided for the DMC review. The external Statistical Analysis Center statistician/analyst will generate the unblinded reports and confidentially distribute the unblinded reports to DMC members. Study team will remain blinded to study treatment until the planned unblinding occurs. The DMC will be conducted to maintain study integrity. Details of DMC is included in the DMC charter.

#### **4.9. Changes to Protocol-Planned Analyses**

The changes to the analyses described in the protocol are listed in the Version History section.

## 5. Sample Size Determination

Approximately 670 participants will be randomly assigned to LY3209590 and insulin glargine in a 1:1 ratio. With the assumption of 15% dropout at Week 26, approximately 284 participants on LY3209590 and 284 participants on insulin glargine will complete 26 weeks of treatment.

The primary objective of this study is to test the hypothesis that LY3209590 is noninferior to insulin glargine on glycemic control as measured by change from baseline at Week 26 in HbA1c in participants with T2D currently on basal insulin and at least 2 injections per day of prandial insulin.

Assuming an NIM of 0.4%, no true difference between treatment groups, and a SD of 1.1%, 568 completers (284 on each of LY3209590 and insulin glargine) will provide greater than 99% statistical power to show noninferiority of LY3209590 compared to insulin glargine using the upper limit of a 2-sided 95% CI of (LY3209590 – insulin glargine). This sample size also has at least 90% statistical power to show noninferiority of LY3209590 compared to insulin glargine using a 0.3% NIM at Week 26.

The 568 completers will provide 90% statistical power to demonstrate the superiority (LY3209590 vs insulin glargine) of change in HbA1c from baseline at Week 26 (assuming a SD of 1.1% and true mean difference is -0.3%) using t-test at alpha of 0.05.

The 568 completers will provide 90% statistical power to demonstrate the superiority (LY3209590 vs insulin glargine) on percentage of participants achieving HbA1c <7% at Week 26 without nocturnal hypoglycemia (<54 mg/dL [3.0 mmol/L] or severe) during treatment phase up to Week 26 using a Fisher's Exact test assuming 28.7% of insulin glargine patients achieve this target and 42% of LY3209590 patients achieve this target.

The 568 participants will provide approximately 83% statistical power to show the superiority of the event rate of clinically significant nocturnal hypoglycemia (<54 mg/dL [3.0 mmol/L] or severe) during treatment phase up to Week 26 (assuming event rate of 0.55 [SD=2.6] and 1.1 [SD=2.6] events per participant per year for LY3209590 and insulin glargine, respectively, representing a 50% decrease in event rate for LY3209590 over insulin glargine) using a negative binomial distribution at alpha = 0.05.

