## 9.3. Statistical Analyses

### 9.3.1. General Considerations

Statistical analysis of this study will be the responsibility of Lilly or its designees. Any change to the data analysis methods described in the protocol will require an amendment ONLY if it changes a principal feature of the protocol. Any other changes to the data analysis methods described in the protocol, and the justification for making the change, will be described in the SAP or the clinical study report. Additional exploratory analyses of data will be conducted as deemed appropriate.

Unless otherwise stated, the efficacy and safety analyses will be conducted on either EAS1 or EAS2, and the safety analyses will be conducted on the SS. All tests of treatment effects using statistical models will be conducted at a 2-sided alpha level of 0.05 and 2-sided 95% CI will be provided.

Unless otherwise specified, the other secondary and tertiary efficacy measures will be analyzed using the data up to the discontinuation of study treatment (EAS2), defined by the date of last study dose + 10 days or the initiation of rescue therapy, whichever is earlier.

Handling of missing, unused, and spurious data are addressed prospectively in the overall statistical methods described in the protocol and in the SAP, where appropriate. Adjustments to the planned analyses are described in the final CSR.

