Event rate of Level 1 hypoglycemic events (events/participant/year): • All documented	Baseline, 0-6, 0-12, 0-26, 12-26 weeks, post-treatment period	Negative binomial regression with treatment, baseline HbA1c and baseline Level 1 hypoglycemia rate as covariates, log (exposure/365.25 days) as the offset in the model.
Event rate of Level 2 hypoglycemic events (events/participant/year): • All documented	Baseline, 0-6, 0-12, 0-26, 12-26 weeks, post-treatment period	Negative binomial regression with treatment, baseline HbA1c and baseline Level 2 hypoglycemia rate as covariates, log (exposure/365.25 days) as the offset in the model.

Endpoint	Analysis Period	Statistical Method
Event rate of Level 3 hypoglycemic events (events/participant/year): 
 
• All documented
 
	Baseline, 0-26 weeks, post-treatment period	Negative binomial regression with treatment, baseline Level 3 hypoglycemia rate and baseline HbA1c as covariates, log (exposure/365.25 days) as the offset in the model.  If the number of events is too small to run the negative binomial regression, exposure adjusted rate calculated by total number of events divided by total exposure for individual patients) will be provided and the empirical method (see Appendix 11 (Section 6.11) for details) will be used for treatment comparison.
Event rate of Level 2/3 hypoglycemic events (events/participant/year): 
 
• All documented
 
• Nocturnal
 
• Non-nocturnal
 
	Baseline, 0-6, 0-12, 0-26, 12-26 weeks, post-treatment period	Negative binomial regression with treatment, baseline HbA1c and baseline hypoglycemia rate of the same hypoglycemia type as covariates, log (exposure/365.25 days) as the offset in the model.  The plots of the mean cumulative functions (MCFs) by each treatment arm will also be created. The population mean for cumulative number of events up to time t, $M(t)$ , will be estimated using a nonparametric estimation method described by Nelson (2003).
Incidence of Level 1 hypoglycemic events: 
 
• All documented
 
	Baseline, 0-6, 0-12, 0-26, 12-26 weeks, post-treatment period	Logistic regression with treatment, baseline HbA1c and baseline Level 1 hypoglycemia incidence as covariates.

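### The stated power of approximately 83% for the nocturnal hypoglycemia rate does not follow from the two printed SDs of 2.6; used together they give about 52% to 74%.

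*SAP*

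**What the plan says.** SAP 5 and Protocol 9.5 carry the same power statement for this endpoint. The claim is that "The 568 participants will provide approximately 83% statistical power to show the superiority of the event rate of clinically significant nocturnal hypoglycemia". The inputs are given as "assuming event rate of 0.55 [SD=2.6] and 1.1 [SD=2.6] events per participant per year for LY3209590 and insulin glargine", described as "representing a 50% decrease in event rate for LY3209590 over insulin glargine", and the calculation is said to be made "using a negative binomial distribution at alpha = 0.05".

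The 568 are the expected completers: "approximately 284 participants on LY3209590 and 284 participants on insulin glargine will complete 26 weeks of treatment". The endpoint covers the treatment phase up to Week 26, so exposure is half a year. The power sentence does not give the sidedness, but Protocol 9.3.1 does: "All tests of treatment effects using statistical models will be conducted at a 2-sided alpha level of 0.05". The planned analysis for Level 2/3 events, including nocturnal ones, is in SAP 4.6.2.2.1: "Negative binomial regression with treatment, baseline HbA1c and baseline hypoglycemia rate of the same hypoglycemia type as covariates", with log exposure as offset.

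Neither document gives a dispersion parameter. Neither says whether the SD of 2.6 belongs to one-year counts, to the underlying participant rates, or to annualised rates observed over 26 weeks.

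**The concern.** A negative binomial model ties the variance to the mean. The same SD at means of 0.55 and 1.1 therefore cannot come from one dispersion value, and it forces a very large dispersion in the LY3209590 arm. That dispersion inflates the variance of the log rate ratio, so the stated power looked too high for the stated inputs.

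The nocturnal event rate is one of three key secondary endpoints under alpha control, and both documents present its power as a property of the design. If the SDs are right, the chance of showing a true halving of the rate is well below what is claimed. If the power is right, a printed SD is wrong. A reader cannot tell which.

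**Working it through.** **Inputs.** Rates 1.1 (glargine) and 0.55 (LY3209590) per year, SD 2.6 in each arm, n = 284 per arm (all SAP 5); t = 0.5 year (26 weeks); two-sided alpha 0.05 (Protocol 9.3.1).

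**Sidedness, checked on a figure that does reproduce.** HbA1c superiority in the same section (difference 0.3, SD 1.1, 284 per arm): 0.3 / (1.1 × √(2/284)) = 3.250, and Φ(3.250 − 1.96) = 90.1%. The plan states 90%. One-sided would be 94.6%. The Fisher figure for the composite endpoint also matches only two-sided (90.0%, against 94.6% at alpha 0.10). Alpha in this section is therefore two-sided 0.05.

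**Dispersions implied by SD 2.6.** With mean μ, k is

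- one-year counts: (SD² − μ)/μ²
- underlying rates: SD²/μ²
- annualised 26-week rates: (SD² − μ/t)/μ²

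**Attempt to reproduce 83% by Wald test, both SDs.** Var(log RR) = [1/(1.1t) + k₀ + 1/(0.55t) + k₁]/n, where k₀ is glargine and k₁ is LY3209590. Power = Φ(ln 2/√Var − 1.96). For one-year counts, Var = (1.818 + 4.678 + 3.636 + 20.529)/284 = 0.1080, SE = 0.3286, and Φ(0.6931/0.3286 − 1.96) = 55.9%.

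| What the SD describes | k₀ | k₁ | Wald power | Simulated, common dispersion fitted |
|---|---|---|---|---|
| One-year counts | 4.68 | 20.53 | 55.9% | 70.6% |
| Underlying rates | 5.59 | 22.35 | 52.5% | 66.1% |
| Annualised 26-week rates | 3.77 | 18.71 | 59.9% | 74.2% |

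The simulations used 5,000 trials per setting (Monte Carlo SE about 0.6 points). Counts were drawn with the arm-specific dispersions and fitted with treatment only, because the plan gives no covariate effects. Repeat runs agreed within about 1.5 points. In the first setting the mean model SE (0.274) was below the true SD of the estimate (0.333), so 70.6% is on the optimistic side.

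A two-means test with SD 2.6 gives 0.55/(2.6 × √(2/284)) = 2.52 and a power of about 71%.

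**What does come near 83%.** Each of these departs from the printed text.

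| Departure | Power |
|---|---|
| Glargine k in both arms (one-year counts / underlying rates / annualised rates) | 85.9% / 81.7% / 90.0% |
| k = 6.76 (that is, 2.6²), 284 per arm, a full year of exposure | 82.6% |
| k = 6.76, 335 per arm, 26 weeks | 83.0% |

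The first row implies an LY3209590 SD of 1.40 / 1.30 / 1.50, not 2.6. With k = 6.76 at the stated 284 per arm and 26 weeks, power is 76.5%. Other departures may exist.

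**Size of the mismatch on the SD scale.** With the glargine SD kept at 2.6, a Wald power of 83% needs k₁ = 5.94 / 5.03 / 6.84, which is an LY3209590 SD of about 1.53 / 1.23 / 1.78.

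**The case against.** The strongest reply is that 83% is recoverable and probably sound. The planned regression has no arm-specific dispersion, so one common dispersion is a natural planning input. Taking k = 2.6²/1.1² = 5.59 from the glargine arm, with a pooled-rate null variance, gives 82.7% at 284 per arm, 26 weeks and two-sided 0.05. This is plausible, and it would mean that the second SD was misprinted. But it sets aside the printed LY3209590 SD, so it explains the disagreement without removing it. The documents do not show that this was the calculation.

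A second reply is that 52% to 74% is not a strict bound. One dispersion taken at the mean rate of 0.825 can reach 76% under the annualised reading. That dispersion (7.51) gives SDs of √(1.1 + 7.51 × 0.55²) = 1.84 and √(2.2 + 7.51 × 1.1²) = 3.36, so it does not honor 2.6 in each arm. If 2.6 were the SD of the 26-week count, power would be about 20% to 38%, but the SD is printed beside a per-year rate. The range therefore holds for the three readings named. It is right that its lower part comes from arm-specific dispersions; under a fitted common dispersion the figures are 66% to 74%.

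Third, hypoglycemia is analyzed on the Safety Analysis Set with an exposure offset, so more than 568 participants can contribute. Even at 335 per arm with full exposure, an upper limit, both SDs give 59% to 67% (Wald) or at most about 80% (simulated). Covariate adjustment may add power, but nothing in the plan allows the gain to be quantified.

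It also stands that no decision rule depends on the 83%.

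**Conclusion.** The printed inputs and the printed power disagree. With both SDs of 2.6, 284 per arm, 26 weeks and two-sided 0.05, power is about 52% to 60% (Wald, arm-specific dispersions) or 66% to 74% (simulated, common dispersion), which is 9 to 31 points below the stated figure. This rests on reading the SD as one of three per-year quantities and on crediting nothing for covariates.

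It does not show that the trial is underpowered for this endpoint. If the LY3209590 SD was misstated and a common dispersion near the glargine value was intended, the power may be near 83% or higher. The statement should be corrected because it concerns an alpha-controlled endpoint and appears in both documents.

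**What to change.** In Protocol 9.5 and SAP 5, either replace the SD of 2.6 common to both arms with the dispersion parameter actually assumed, or correct the LY3209590 SD. State what any remaining SD describes, the 26-week exposure, the n used, that alpha is two-sided, and the calculation method. Then restate the power that follows. If both SDs of 2.6 are kept, the figure should come down to about 52% to 74%, depending on the SD reading and the method named.

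The cost is revised text in two sections. The power figure falls if both SDs are kept; it may stay near 83% or rise if the LY3209590 SD or the dispersion was what was misstated. The sample size, the primary-endpoint power and the planned analysis do not change.

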## 6. Supporting Documentation

### 6.1. Appendix 1: Demographic and Baseline Characteristics

Demographic and baseline characteristics including but not limited to age (years), age groups ( $<65$ ,  $\geq 65$  and  $<75$ ,  $\geq 75$  and  $<85$ ,  $\geq 85$  years), sex, ethnicity, race, country, region, height, weight (kg), body mass index (BMI: kg/m^2), BMI groups ( $<25$ ,  $\geq 25$  and  $<30$ ,  $\geq 30$  and  $<35$ ,  $\geq 35$  kg/m^2), eGFR groups ( $<30$ ,  $\geq 30$  and  $<60$ ,  $\geq 60$  and  $<90$ ,  $\geq 90$  mL/min/1.73 m^2), duration of diabetes (years), HbA1c at screening, HbA1c stratum at screening ( $<8.0\%$  and  $\geq 8.0\%$ ), baseline HbA1c, baseline HbA1c stratum ( $<8.0\%$  and  $\geq 8.0\%$ ), baseline fasting serum glucose (mmol/L and mg/dL), type and category of pre-study basal insulin type of pre-study prandial insulin (type, category and frequency), prandial insulin dosing plan (carbohydrate counting: Yes or No), use of prandial insulin correction factor, GLP-1 RA use, baseline noninsulin antihyperglycemic medications (type and number), baseline FBG  $<120$  mg/dL (based on the study-provided glucometer), and routine use of personal CGM or FGM at randomization will be summarized by treatment group using the mITT and Randomized Population (if different from the mITT).

Continuous measures will be summarized using descriptive statistics and treatment difference will be analyzed using the analysis of variance. Categorical measures will be summarized using sample size, frequency, and percentage and treatment difference will be analyzed using Chi-squared test.

The by-participant listing of demographic and baseline characteristics will be provided for Randomized Population.

Historical conditions are conditions that end prior to inform consent and preexisting conditions are conditions that are still ongoing at inform consent. The number and percentage of participants with historical conditions will be summarized by treatment group using MedDRA PT using the mITT and Randomized Population (if different from the mITT). Events will be ordered by decreasing frequency. Similar summary will also be provided for preexisting conditions.

### 6.2. Appendix 2: Treatment Compliance

Treatment compliance will be summarized using mITT population excluding inadvertently enrolled participants .

The study protocol provides dosing algorithm for both study treatments (LY3209590 and insulin glargine). The investigator will calculate algorithm recommended dose based on the participant fasting blood glucose and hypoglycemia occurrence reported in e-diary. If the investigator does not agree with the algorithm recommended dose, the investigator will prescribe another dose for the participant and choose the reason for not following the algorithm recommended dose from a pick-list. The number and percentage of investigator prescribed doses different from algorithm recommended dose will be provided to evaluate the adherence of algorithm dose. The reason of not following the algorithm recommended dose will also be summarized.

Study personnel or the participant will administer the first study dose of LY3209590 at the site. Insulin glargine can be taken at the site or after the visit depending upon whether the study visit timing coincides with the participant's usual time to administer basal insulin. The subsequent doses are self-administered. To access the adherence of treatment administration, the number and

percentage of investigator prescribed doses that are not equal to participant administered dose will be provided.

